1.1. Study Title

Leveraging Social Networks to Increase COVID-19 Testing Uptake: A Comparison of Credible Messenger and Chain Referral Recruitment Approaches

1.2. Is this study exempt from federal regulations?

No

1.3. Exemption Number

NA

1.4. Clinical Trial Questionnaire

1.4.a. Does the study involve human participants?

Yes

1.4.b. Are the participants prospectively assigned to an intervention?

Yes

1.4.c. Is the study designed to evaluate the effect of the intervention on the participants?

Yes

1.4.d. Is the effect that will be evaluated a health-related biomedical or behavioral outcome?

Yes

1.5. Provide the ClinicalTrials.gov Identifier for this trial, if applicable

NCT04873401

Statement of Compliance

New York State Psychiatric Institute (NYSPI) Institutional Review Board (IRB) is duly constituted, has written procedures for initial and continuing review of clinical trials; prepares written minutes of convened meetings, and retains records pertaining to the review and approval process; all in compliance with requirements of FDA regulations 21 CFR Parts 50 and 56, HHS regulations 45 CFR 46, and International Conference on Harmonization (ICH) E6, Good Clinical Practice (GCP), as applicable.

Investigator's Signature

X

20 January 2023

Section 2. Study Population Characteristics

Introduction:

Study Rationale

COVID-19 has severely impacted underserved populations and their communities. Higher incidence of COVID-19, hospitalization and mortality, have been found in neighborhoods in NYC with high poverty rates, where HIV, HCV, opioid use and justice involvement/arrests are endemic. In Harlem, Washington Heights, and the South Bronx, where the proposed supplement will take place, rates of infection and mortality were some of the highest in NYC. Historically, those who use opioids and other substances inconsistently accessed services due to a confluence of structural (e.g., housing instability, stigma, discrimination, and lack of insurance) and individual-level factors (e.g., mental illness; medical mistrust). Identification of positive cases requires widespread testing of this vulnerable yet “hidden” population.

Guided by social cognitive theory (SCT), Andersen’s model of health care access and the EPIS framework, Specific Aims are: 1) Adapt two implementation strategies to support COVID-19 testing uptake and sustainability, adapting elements of existing efficacious social network-based interventions via a CBPR approach. 2) Examine and compare the efficacy of two sets of implementation strategies on (i) reach, (ii) testing uptake, (iii) service delivery (i.e. quarantine, medical care, contact tracing) and (iv) sustainability for individuals who use opioids and other drugs. Use of data drawn from Healthix, a public health information exchange, will supplement this comparison by generating a baseline of participant prior testing and health behavior to determine access to underserved populations as well as long-term influence on future testing behavior. 3) Elucidate and compare the system/organizational-, staff-, and individual-level factors that influence implementation (i.e. fidelity, acceptability, feasibility, sustainability) of the strategies to develop a plan for dissemination and scale-up in other CBOs who serve opioid and other substance using individuals in NYC.

Background

2.1.1. Conditions or Focus of Study

Condition 1: COVID-19

Condition 2: Substance use

Condition 3: Opioid Use

2.1.2. Study Aims

Following a CBPR approach that builds on the expertise and community outreach infrastructure of Argus and Alliance, we propose to adapt two implementation strategies that have been proven to increase the reach, access, and uptake of HIV testing and related services in order to support the uptake and sustainability of point-of-service (POS), onsite COVID-19 testing in CBOs that target underserved people who use opioids and other substances. Guided by social cognitive theory (SCT), Andersen's model of health care access and the EPIS framework, the specific aims are to:

Aim 1. Adapt two implementation strategies to support COVID-19 testing uptake and sustainability, adapting elements of existing efficacious social network-based interventions via a CBPR approach.

Aim 2. Examine and compare the efficacy of two sets of implementation strategies on (i) reach, (ii) testing uptake, (iii) service delivery (i.e. quarantine, medical care, contact tracing) and (iv) sustainability for individuals who use opioids and other drugs. Use of data drawn from Healthix, a public health information exchange, will supplement this comparison

by generating a baseline of participant prior testing and health behavior to determine access to underserved populations as well as long-term influence on future testing behavior.

Aim 3. Elucidate and compare the system/organizational-, staff-, and individual-level factors that influence implementation (i.e. fidelity, acceptability, feasibility, sustainability) of the strategies to develop a plan for dissemination and scale-up in other CBOs who serve opioid and other substance using individuals in NYC. This investigation will provide much needed information to improve health outcomes and to identify effective system-level responses to prevent or arrest the spread of COVID-19 among the social networks of those who use opioids and other substances, a highly vulnerable and often overlooked population.

2.2. Eligibility Criteria

Sample 1: Testing Participants. Must endorse opioid or other substance abuse in the past 6 months and must speak English or Spanish; >18years.

Sample 2: Staff Participants. Currently employed at either Argus or Alliance, including POLs participating in Peer programs. PI/PD will present the study to staff and interested staff will be asked to contact the research team.

2.3. Age Limits

Samples 1-2

Minimum: 18 years

Maximum: NA

2.4. Inclusion of Women, Minorities and Children

Inclusion of Women. There is no inclusion or exclusion of participants based on gender. Based on demographic and community/area data of Argus and Alliance clients, staff, and credible messengers we anticipate females will comprise approximately 40% of the sample.

Inclusion of Minorities. We will not exclude participants based on ethnicity. Based on the demographic data of Argus and Alliance clients, staff, and credible messengers we anticipate 51% African American and 39% will be Hispanic.

Inclusion Across the Lifespan. Children will not be enrolled. The proposed study involves those who are using opioids and other drugs and who are largely underserved and at risk for COVID-19 infection. In NYS, the current

opioid epidemic does not center on those younger than 18 and currently, those at greatest risk for negative sequelae from complications due to COVID-19 are older than 18.

2.5. Recruitment and Retention

Recruitment of agency staff and credible messengers for staff surveys and focus groups. All agency staff will be invited to participate in the staff surveys; those staff and credible messengers directly involved in the recruitment strategies and on-site COVID-19 test delivery, either via educating testing participants and supervising credible messengers (staff) or recruiting peers in the community (credible messengers) will be invited to participate in the staff surveys and focus groups in the same way. The PI/PD will present the study to agency staff both in-person at a staff meeting and via email and interested staff will be asked to contact the research team. An email from the PI (with an attached information sheet) explaining the project and staff participation in the survey and focus group will be sent to agency leadership who will then distribute it to staff and Credible Messengers. These methods have been used successfully in our prior work with probation offices and treatment staff. The email will instruct interested staff to contact research staff directly to ask questions. For those interested in participating in focus groups, efforts will be made to schedule interviews at times that do not interfere with staff roles (e.g. lunch breaks; staff meetings). Considerable effort will be taken to ensure that staff do not feel coerced to participate. It will be emphasized to staff that participation (Y/N) is voluntary and will in no way affect their employment status. These procedures have been successfully used in PIs prior work recruiting justice and treatment staff. Retention and engagement activities will include small thank you gifts for participation in surveys, one at baseline and the other after study activities have been completed. We are unable to address staff-turnover which may impact on study retention.

Recruitment of testing participants. Testing participants will be recruited in one of two ways: chain referral and credible messenger. In the chain referral strategy, an initial set of n=8 “seed” participants are recruitment by staff of eligible clients receiving services at Argus and Alliance (n=16 total seeds). For clinic-based recruitment of “seeds”, participants will be recruited from among those individuals who use opioids and other drugs who are receiving services through Argus or Alliance; services do not need to be substance use related. (Following a brief training, these “seed” participants then recruit additional participants (“peer recruits”) from among their own peer networks of those known to use opioid or other drugs in community settings (peer- recruitment). “Seed” participants are given three unique, numbered coupons, which they can give to people they know (peers) who are also use opioids and other drugs. The coupons will have information, by which peers who are interested in participating in the study can contact the research team to be screened for eligibility. Participants will receive renumeration for each peer recruit who enrolls in the study by redeeming a coupon given to them by that participant. Peer-recruits then repeat the same process with members of their peer network.

The credible messenger strategy involves leveraging the existing infrastructure at both Argus and Alliance, which includes credible messenger programs that are well-established, with considerable influence and impact within the respective communities served by these two agencies. The credible messengers within these programs have been trained to conduct community outreach to target individuals at increased risk for HIV, STIs, HCV and SUD and encourage testing and/or linkage to services. Interested credible messengers (n=4 from each site) will serve as messengers in the current study and will be trained to also include education about COVID-19, ways to reduce risk as well as ways to increase motivation to test for COVID-19 at the respective clinics. Credible messengers will conduct community outreach, targeting those locations and venues where potentially credible participants are located, and will provide education and encourage these individuals to seek testing. The potential participants will be given a coupon which will be redeemed at the clinic when the participant is enrolled in the study after being determined as eligible.

As testing participants are assessed once and then offered a test immediately thereafter, study retention is not a considerable focus of procedures. Participants recruited by chain-referral will be given a brief survey following their recruitment efforts to document number of attempts, time etc. This brief survey will occur at the visit when the participant comes to the clinic to receive payment for redeemed coupons that s/he distributed to peers; it is anticipated the payment will serve to adequately retain participants for the purpose of completing the brief survey.

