Testing Participants. We anticipate enrolling n=500 participants across both strategies in an 8 month period of time. Based on demographic characteristics of the neighborhoods where recruitment will occur in addition to current demographics of the substance using clientele of Argus and Alliance, we anticipate participants will comprise 64% male, 51% African American, 28% Hispanic. Inclusion/exclusion criteria. All participants, regardless of recruitment strategy, must 1) be >18 years of age; 2) endorse opioid or other substance abuse in the past 6 months, and 3) speak English or Spanish. Those who deny history of substance use (but will be offered COVID-19 testing), or present with intoxication that prevents meaningful study participation at the time of enrollment will be excluded. Individuals too intoxicated to participate, but otherwise willing and eligible will be rescheduled up to two times. Finally, those recruited by peer chain referral (see 3.7.2) who test positive for COVID-19 will be excluded from participating in the recruitment of other individuals until such time as they receive a negative nucleic acid COVID-19 test. This more stringent assessment of non-infectiousness is being used given the likely inclusion of immunocompromised individuals in the study groups.

Agency staff and credible messengers. We will enroll n=2 staff and n=8 credible messengers across both sites. Based on current staffing demographics we anticipate staff will be 50% female, 50% Hispanic; 50% white, and credible messengers will be 63% male; 70% Hispanic; 60% White. Inclusion/exclusion criteria: staff must be 1) >18 years old; 2) employed by either Argus or Alliance

3.1.1(b) Study Procedures, Materials, and Potential Risks

Research data will be drawn from 1) self-completed questionnaires, 2) staff focus groups, 3) participant responses to process measures, 4) Healthix health data management information system, 5) analysis of saliva

Phase 2.

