Written informed consent will be obtained from all testing participants at the time of enrollment. The consent process will take place in a private office at either alliance or Argus without any agency staff present. Potential participants will be assured that their decisions about participation (yes or no) will in no way affect current or future services received at these agencies. Consent will be obtained either by RAs. Potential participants will be observed for signs of active intoxication that might interfere with their capacity to meaningfully consent to participation (e.g. excessive drowsiness, slurred speech, etc.). For those who are excluded due to excessive intoxication, clinical staff will be notified immediately, and the individual will be assessed by a medical provider for risk of impending overdose (intranasal naloxone and other supplies for emergency response are readily available at both clinical sites). Appropriate medical care or observation will be provided by clinical staff as indicated based on that assessment. If the individual is not determined to be at immediate risk of overdose, he or she will be asked to reschedule enrollment for a later date. Up to three attempts will be made to obtain informed consent from participants who are excessively intoxicated. If informed consent cannot be obtained by the third attempt due to excessive intoxication, the individual will be excluded from participation.

The consent forms will describe all aspects of the study and explain that confidentiality will be maintained unless concerns about the participant warrants referral to a mental health provider, such as active suicidal or homicidal ideations. Participants will also be notified that we have obtained a Federal Certificate of Confidentiality. This Certificate protects the investigators from having to release the names or other identifying characteristics of research participants. Sufficient time will be allowed for questions about the consent forms or about the study in general. The consent forms will also specify the expected range of financial incentives for study participation. At the time of enrollment, participants will also be asked to provide consent for disclosure of HIPAA-protected health information (PHI) located in Healthix. All consent forms for all phases of study participation will be developed in accordance with the Internal Review Board (IRB) at New York State Psychiatric Institute.

3.1.2(b) Protection Against Risk

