3.3.2 Data Monitoring

Interim Analysis Plans: The DSMB will review safety reports quarterly (see below). More frequent meetings will be scheduled if indicated by interim findings. A written summary will be submitted to the IRB following each meeting.

The data analyst will conduct interim analyses quarterly to verify that recruitment is consistent with projections. To support ongoing quality assurance and uniformity in data collection, interim analyses will also be conducted to examine patterns of missing data from surveys. Analyses to assess the psychometric properties of the measures will be conducted following the first implementation cycle. These data will be made available to the DSMB. In addition, data from the Site Recruitment Monitoring Form will be made available to the DSMB for monitoring of recruitment and participation rates for all assessments, as well as refusal and attrition rates and study progress.

Stopping Rules: This study will be stopped prior to its completion if: (1) the intervention is associated with adverse effects that call into question the safety of the intervention such as increased rates of COVID-19 infection; (2) difficulty in study recruitment or retention, or enrollment of participants will significantly impact the ability to evaluate the study endpoints; (3) any new information becomes available during the trial that necessitates stopping the trial; or (4) other situations occur that might warrant stopping the trial.

3.3.3 Management and Reporting of Adverse Events (AEs), Serious Adverse Events (SEAs) and Unanticipated Problems (UP).

This study will use the NIH Reportable Events Policy definition of Adverse Events (AEs), Serious Adverse Events (SAEs) and Unanticipated Problems Involving Risk to Subjects (UP).

We will define and measure risk as indicated in the table below.

Table 3.3a. Method of Ascertainment of Serious and Adverse Events, and Unanticipated Problems for STAFF (Sample 2)

oh

Reportable Event	What they are in the study	Method of Ascertainment	Reporting Requirements		
			IRBs	PSMB	NIDA PO
Death	- Employee/staff death during study operations	We will ask peer supervisors, site coordinators and agency leadership to report any deaths as soon as they learn of them.	ASAP, but no later than 3 working days	Immediately	ASAP, but no later than 3 working days

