4.3. Outcome Measures

Table 5. Outcome Measures

Name	Type	Time Frame	Description
Reach	Primary	Baseline	# of coupons redeemed; (secondary # redeemed/# distributed)
Testing Uptake	Primary	Baseline	Y/N; (secondary # redeemed/# distributed)
Service Delivery (exploratory): Quarantine Medical care Contact tracing	Primary	Baseline	For positive test results only: Y/N self-quarantine Y/N (date 1st apt) Y/N (Agreed to provide names/addresses of network)

Acceptability; Sustainability	Primary	Baseline	Continued recruitment; testing beyond Implementation phase
Feasibility	Primary	Baseline	Recruitment and testing delivery facilitators and barriers;
Fidelity	Primary	Baseline	Recruitment and testing protocol TBD during Phase 1
Organizational Climate, support and functioning, leadership	Secondary	Baseline and post implementation	Innovation/Flexibility; Organization support; Communication, Job satisfaction
Staff Demographics	Secondary	Baseline and post implementation	Gender, age, race/ethnicity, position, job tenure, education
COVID-19 knowledge /attitudes	Secondary	Baseline and post implementation	a) knowledge of symptoms b) subjective effectiveness of safety practices c) subjective safety/unsafe of activities d) vaccination acceptability e) COVID-19 stigma
Perceived potential sustainability of testing program	Secondary	Baseline and post implementation	Program Sustainability Assessment Tool: Political support, Partnerships, Capacity, Evaluation, Communications, (20 items; (.79-.92)

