4.5 Statistical Analyses

4.5.1 Analysis overview and main outcomes. The primary outcome of interest comparing the strategies will be testing occurrence (yes vs. no) as an indicator of testing uptake. An important secondary outcome will be reach measured through the number of coupons redeemed. Prior to the main analysis, all variables will be examined for distribution and outliers. Continuous outcomes will be described through means and standard deviations, while dichotomous and categorical outcomes will be described through proportions.

4.5.2 Statistical analysis for Aim 2. Models that compare the effect of recruitment strategy on outcomes related to reach, testing uptake, and service delivery will adjust for measures assessed at baseline (e.g., baseline substance use, testing history). For our primary (dichotomous) outcome (testing uptake) logistic regression will be used: $\text{logit}(\text{pi}) = \beta_0 + \beta_{\text{RecStr}}(\text{Recruitment Strategy})_{ii} + \beta_{\text{Site}}(\text{Site})_{ii} + \beta_{\text{SubUse}}(\text{Substance Use})_{ii} + \beta_{\text{TestHis}}(\text{Testing History})$, thus be β_{RecStr} which will estimate the differential effect of chain-referral vs. POL recruitment on testing uptake. The model will be adapted for secondary outcomes. Sensitivity analyses will stratify the analyses by time to determine if recruitment strategy effects differed before and after the cross-over. Demographic characteristics and other variables related to the Andersen, SCT, and EPIS models will be examined as potential mediators/moderators.

4.5.3 Statistical analysis for Aim 3. Implementation features related to acceptability, sustainability, feasibility, and fidelity will be assessed at both the staff- and individual-level. As an illustrative example, we will consider whether participants endorse time constraints and the association with testing uptake. The logistic model will take the form $\text{logit}(\text{pi}) = \beta_0 + \beta_{\text{RecStr}}(\text{Recruitment Strategy})_{ii} + \beta_{\text{Site}}(\text{Site})_{ii} + \beta_{\text{TimeCon}}(\text{Time Constraint})_{ii}$ where pi is the probability of being tested post-recruitment for the i^{th} individual. This model assesses the effect of a time barrier on the likelihood of getting testing while controlling for the differing recruitment strategies and sites.

4.6. Subject participation duration:

N/A

4.7. FDA regulated intervention:

No

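### Reach counts coupon-holders who enrol in the research, not eligible people brought to the clinic, so unequal refusal between strategies would bias the reach comparison

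*Combined protocol and SAP*

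**What the plan says.** Table 5 (4.3) defines reach as the number "of coupons redeemed; (secondary # redeemed/# distributed" as its secondary form) and labels it Primary. Section 4.5.1 ranks it lower: "An important secondary outcome will be reach measured through the number of coupons redeemed".

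Sections 2.5 and 3.1.1(a) describe when a coupon is redeemed, in the same terms in both places:

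- **Credible messenger.** Contacts are given a "coupon which will be redeemed at the clinic when the participant is enrolled in the study after being determined as eligible". The messenger's task is to educate people and urge them to get tested. The wording on this coupon is not given.
- **Chain referral.** The coupon carries information by which "peers who are interested in participating in the study can contact the research team to be screened for eligibility". The recruiter is paid for each peer who enrols with a coupon, and enrolled peers then receive coupons and repeat the process.

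For participants, consent, enrolment and a survey come before the test (3.1.1(b)), and consent to Healthix disclosure is requested at enrolment (3.1.2(a)). Section 3.1.2(a) also promises that a decision about participation "will in no way affect current or future services received at these agencies". No rule says how to count an eligible person who presents a coupon and then declines the research.

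**The concern.** The trial asks which strategy is better at reaching people who use drugs and getting them tested (Justification for Intervention; 3.1.4). The agencies are then to carry on with the strategy that proves efficacious (Phase 3), and 4.8 plans to scale it up. A count taken at enrolment mixes two things: how many eligible people a strategy brings in, and how many of those agree to join a study. Only the first would matter to an agency running the programme outside research.

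The loss would do no harm to the comparison if it were the same in both strategies. The text gives two reasons why it may not be. In chain referral, enrolling pays the person who handed over the coupon and opens the same opportunity to the new enrollee. No such recruitment reward is described for messengers' contacts. The message also differs: chain-referral coupons point to the study, and messengers point to the test. If messengers' contacts decline more often for these reasons, scored reach would lean towards chain referral, which 4.4.1 hypothesises to be better.

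**Working it through.** **The plan's own figure.** The only power statement (4.2) concerns testing uptake: 7.8% vs 16.1%, 250 per strategy, alpha 0.05. A two-sided pooled normal approximation gives 81.4% power using the unrounded 7.8422%. The odds ratio is (0.161/0.839)/(0.078/0.922) = 2.27. Both agree with the plan. Neither bears on reach, for which the plan states no power or sample size.

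**Inputs for reach**

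- Scored reach is redeemed coupons, and redemption requires enrolment (2.5, 3.1.1(a), Table 5).
- Assumption: 250 eligible coupon-holders attend under each strategy, so true reach is equal. This borrows the planned number per strategy as a convenient scale.
- Assumption: the share who attend but decline is d_C in chain referral and d_M in credible messenger. The documents give no value. The range shown is 0–10% for d_C and 5–30% for d_M.

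**Formulas**

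- Scored reach = 250 × (1 − d)
- Apparent ratio, chain referral to messenger = (1 − d_C)/(1 − d_M)
- Rough Poisson contrast: z = (a − b)/√(a + b), where a and b are the two scored counts

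| d_C | d_M | Scored reach, C vs M | Ratio | z |
|---|---|---|---|---|
| 5% | 5% | 237.5 vs 237.5 | 1.00 | 0.00 |
| 10% | 10% | 225 vs 225 | 1.00 | 0.00 |
| 10% | 5% | 225 vs 237.5 | 0.95 | −0.58 |
| 0% | 10% | 250 vs 225 | 1.11 | 1.15 |
| 5% | 20% | 237.5 vs 200 | 1.19 | 1.79 |
| 0% | 20% | 250 vs 200 | 1.25 | 2.36 |
| 10% | 30% | 225 vs 175 | 1.29 | 2.50 |

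For the 0% vs 20% row: 250 × 0.80 = 200; 250/200 = 1.25; z = 50/√450 = 2.36.

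**Reading the table.** Equal refusal gives no bias, and higher refusal in chain referral reverses its direction. Counting at presentation gives 250 vs 250 in every row. The ratio does not depend on the number attending or on clustering. The z values depend on both: they treat people as independent, which recruits within a referral chain are not, so they overstate the evidence. The plan names no test for the count (4.5.2 says only that the model will be adapted for secondary outcomes), so z is a guide to scale only.

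**The case against.** The strongest reply is that the gate is the same in both strategies and that enrolment may be what the sponsor means by reach. The Justification for Intervention glosses reach as recruitment of the target population. This stands in part: decliners are lost in both strategies, and bias needs a difference in refusal that the documents neither state nor rule out. But even on that gloss, one count cannot separate outreach from consent.

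Refusals are also partly tracked. Section 3.3.2 says "data from the Site Recruitment Monitoring Form will be made available to the DSMB" and includes refusal rates. Each site runs one strategy per period, so refusals by site and period are refusals by strategy. This makes the repair easy, but the plan does not link those records to the reach outcome.

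Three stronger readings are tempting, and the documents do not support them.

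- *Only chain-referral coupons invite people into a study.* The messenger coupon's wording is never given, it goes to people described as potential participants, and it is redeemed at enrolment. The documented contrast is in the spoken message and the recruitment reward. Section 3.1.2(a) mentions financial incentives for participation without distinguishing strategies, so taking part may be rewarded in both.
- *People are brought in, tested and then ignored.* Testing without enrolment is stated only for one group: "Those who deny history of substance use (but will be offered COVID-19 testing" is how 3.1.1(a) describes it. They are outside the target population and rightly outside reach. The promise about services does not say that eligible decliners get the study test.
- *Reach is tilted towards chain referral.* That is a plausible direction, not a documented one.

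A further reply is that counting at presentation only moves the gate, since a peer not interested in the study may never attend. That is true, but failure to attend is part of what a strategy achieves, whereas refusing research after arrival is not.

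**Conclusion.** The point holds as a weakness in how reach is defined. In both strategies it counts research enrolments, and the plan gives people different reasons to enrol under each, so a difference in refusal could appear as a difference in reach. Under the assumed range, refusal of 0% vs 10% to 10% vs 30% (chain referral vs messenger) would produce apparent ratios of about 1.1 to 1.3 from equal true reach. Equal refusal would produce none. These sizes rest wholly on assumed refusal shares, and the direction is inference.

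The consequence is limited by the standing of reach: 4.5.1 makes testing occurrence the primary outcome and reach secondary, although Table 5 labels both Primary. It is a worthwhile, inexpensive correction and not a defect that defeats the trial.

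**What to change.** In 2.5, 3.1.1(a) and Table 5:

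1. Log each coupon by number and strategy when it is presented, before consent, with its outcome: ineligible; eligible but declined; enrolled; and, if enrolled, whether tested.
2. Score reach as eligible people presenting a coupon. Report enrolment-based redemption beside it.
3. Report the share of eligible presenters who declined, by strategy, and read the reach comparison in its light.

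Leave payment tied to enrolment as now, and keep a separate term for a presented coupon so that redemption has one meaning. Do not harmonise the coupon wording or contact route, because that would alter the strategies being compared.

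The cost is a coupon-number field on the existing recruitment form and a few lines of protocol and analysis text. Eligibility is already determined before enrolment, and coupons are already recorded electronically (3.3.3.1). People who do not enrol would be known only as anonymous counts, with no survey data and no test results drawn from research records.

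Timing limits what can be done. Section 2.6 gives the status as not recruiting, and Table 1 already tabulates 486 people. If recruitment is complete, the revised count can use only what the Site Recruitment Monitoring Form and coupon records hold. Where they do not separate decliners by strategy, the report should describe reach as enrolment-based and state this limitation.
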